19.2. Secondary Objectives

19.2.1. Secondary Objective # 1

Objective - Implant procedure related information: success rate, implant related times

The Attain Stability Quad LV lead implant success rate will be estimated as the number of subjects with Attain Stability Quad MRI SureScan LV Lead (Model 4798) successfully implanted divided by the total number of subjects who had a Attain Stability Quad MRI SureScan LV Lead (Model 4798) implant attempt. A 2-sided 95% Confidence Interval will be calculated using the Exact Binomial method.

The distribution of implant related times will be summarized through statistical summaries such as mean, standard deviation, minimum, median and maximum. Only subjects with the Attain Stability Quad MRI SureScan LV Lead (Model 4798) successfully implanted will be included in this calculation. The total implant time is defined as time from initial incision to final skin closure. Fluoroscopy time is defined as the total time the fluoroscope is imaging. Cannulation time is defined as the time from insertion of the first CS cannulation catheter to the first successful CS cannulation. Successful lead placement time is defined as the time from lead insertion of the successfully placed lead to the time when the lead is placed in its first acceptable pacing location.

19.2.2. Secondary Objective # 2

Objective - 6-month reliability: post implant lead failure modes

The Attain Stability Quad MRI SureScan LV Lead (Model 4798) is a composite of two existing market released Medtronic products. The helix fixation is identical to the Attain Stability LV Lead Model 20066/4796 (market released outside of the US). The remainder of the lead is similar to the Attain Performa LV Lead Model 4298, released worldwide.

Historical datasets will be used as informative priors for lead related complications. More specifically, analysis of all complications related to fixation (helix performance) will use data from the Attain Stability (Model 20066/4796) research study, conducted outside of the US²¹. Analysis of all other lead related complications will use data from the Attain Performa clinical study, conducted globally. Credible intervals will be constructed for each individual failure mode within the two groups.

Historical Data (for secondary endpoints only)

- Fixation-related LV lead complications - Data from the 37 patients who completed 6-month follow up with a successfully implanted 20066 lead in the Attain Stability study will be used as an informative prior.
- All other LV lead-related complications - Data from the 401 patients who completed 6-month follow up in the Attain Performa 4298 study will be used as an informative prior.

These historical datasets will be down weighted such that their effective sample size will not exceed the 9% of the total sample size (i.e. at most 37 subjects at 6 months).

Statistical Analysis Methods

The weighted historical data will be incorporated using the power prior method²⁴. The weight of the historical data will be adjusted using a loss function²⁵, which scales from 0 to 1 according to the similarity of the historical and observed data. This loss function adjusts the amount of weight the prior receives. The comparison between historical and observed data will be performed twice, once for each group of complications (fixation-related and all other). The objective of using a loss function with the power prior method is to reduce the influence of an informative prior in the parameter estimation, when the historical data does not agree with the current study data.

If analysis of failure rate shows a high level of agreement between historical and current study data or there is better performance for Attain Stability Quad MRI SureScan LV Lead (Model 4798) compared to historical data, the historical data will be weighted at or near a maximum level (9% of total effective sample size). If the Attain Stability Quad MRI SureScan LV Lead (Model 4798) performs worse than historical data, the historical data will receive very little or zero weight. Note that there will be two loss function weights, one for fixation-related complications and one for all other complications. Credible interval calculations will be done separately for individual failure modes within the two groups of complications (fixation and all other).

Denote by θ_c and θ_h the probabilities of lead complication for the current and historical studies respectively. The posterior distributions of θ_c and θ_h respectively, both with minimally informative priors are:

$$\begin{aligned}\theta_c &= \text{beta}(y_c + 1, n_c - y_c + 1) \\ \theta_h &= \text{beta}(y_h + 1, n_h - y_h + 1)\end{aligned}$$

These posterior distributions are then stochastically compared using a posterior Bayesian p-value²⁶ as:

$$p = P(\theta_c \leq \theta_h)$$

The desired characteristics for the loss function are:

1. For $p \geq \sim 0.5$, there is a high level of agreement between current and historical data, therefore the loss function should allow a_0 to be close to 1, allowing for full weight of historical data.
2. Conversely, for $p < \sim 0.5$, there begins to be evidence of disagreement between current and historical data, and a_0 should start to down-weight the prior, i.e. a_0 approaches zero as p approaches zero.

The Weibull cumulative distribution function (CDF) meets these criteria:

$$a_0 = 1 - e^{-(p*5)^2}$$

Note that for the case where the number of samples in the prior is different than the effective number, a scaling factor will be applied, where n_h is the desired effective number of prior samples and N_h is the actual number of prior samples:

[figure not shown]
$$a_0 = \frac{n_h}{N_h} [1 - e^{-(p*5)^2}]$$

Sample values are listed in Table 17 below and illustrated in Figure 7. The comparison between current and historical data will be performed for all LV lead fixation related complications using Attain Stability (Model 20066) historical data and for all other LV lead related complications using Attain Performa historical data.

Table 17: Prior weight from Attain Stability (Model 20066) and prior weight from Attain Performa as a function of the posterior Bayesian p-value (p)

	Prior weight from Attain Stability (Model 20066)	Prior weight from Attain Performa
p	$a_0 = 1 - e^{-(p*5)^2}$	$a_0 = \frac{37}{401} [1 - e^{-(p*5)^2}]$
0.01	0.002	0.000
0.05	0.061	0.006
0.1	0.221	0.020
0.2	0.632	0.058
0.5	0.998	0.092

Figure 7: Loss Function $a_0 = 1 - e^{-(p*5)^2}$

[figure not shown]

Note that the loss function proposed here does not reduce the strength of the prior when the current study outperforms the historical data. This implementation of the loss function is only concerned with negative impacts to patients, i.e. it penalizes an optimistic prior while not penalizing a pessimistic prior.

Also, note that this function is selected for the shape of the CDF rather than due to conventional statistical properties of the Weibull distribution.

Figure 8 illustrates the effect of the power prior coupled with the loss function. The figure shows credible intervals in scenarios where the prior is optimistic (better performance than current study), in agreement (similar performance to the current study), and pessimistic (worse performance than the clinical study). Note that the prior data source in Figure 8 is the Attain Performa study, with 401 patients. As will be discussed later, these data are scaled to represent a maximum of 37 patients (i.e. 9% weight).

Figure 8: Credible Intervals for Scenarios of Agreement Between Historical and Current Data

The prior data set in Figure 8 has 401 samples. However, the maximum effective historical data sample size is $n_h = 37$, for a maximum weight of 9%. Therefore, the prior will be scaled by a factor of $(37/401)$. As an example, illustrated in the middle panel above, if the effective sample size is 34 out of 37, the prior has received 89% of the maximum weight, or 8.5%.

The panels in Figure 8 can be interpreted as follows:

- **Top panel:** The current data shows lower performance than the prior. The loss function produces a substantial penalty resulting in almost no weight to the prior (1%). The posterior (final estimate) is essentially the same as the current study.
- **Middle panel:** The current data is very similar to the prior. The loss function penalty is small, resulting in a prior weight of 8.5% (recall that the maximum weight is 9.2%). Because the agreement is good, the posterior (final estimate) is similar to both the prior and current study.
- **Bottom panel:** The current data is very similar, with slightly better performance than the prior. The loss function produces a weight very close to the maximum of 9.2%. The posterior (final estimate) is a balance between the prior and current study.

Sample Size

A Bayesian adaptive design is set up to enroll patients until a sufficient sample size is achieved to have high probability of meeting the required effective sample size of $n_e = 400$. The number of enrolled patients in the study may vary from 363 to 400 subjects due to the adaptations to the trial. This study follows methods from Berry, et.al.²⁷

The interim analysis will take place after 360 subjects have been enrolled into the study.

The Adaptive Bayesian sample size algorithm will stop or continue enrollment accordingly to the following:

- 1.) If the predictive probability of $n_e \geq 400$ is larger than 80% then enrollment will stop.
- 2.) If the predictive probability of $n_e \geq 400$ is less than 80%, enroll sufficient additional patients to make the probability of $n_e \geq 400$ at least 80%.

At the time of the interim analysis, some patients will not have completed the full evaluation period. A longitudinal model will be employed to enable final observations to be imputed for those subjects with incomplete information.

There are 3 types of subjects at a given interim analysis:

- 1.) Subjects that have complete data
- 2.) Subjects that have partial data (censored value at a particular time)
- 3.) Subjects that have no information (subjects that have not been enrolled)

Predictive probabilities for types 2 and 3 will have to be computed. The predictive probability model that will be used is a piecewise exponential. This will allow the final outcomes for the subjects who have not had an event and have not completed 6 month follow up to be simulated.

Note this Bayesian approach to borrow information from historical datasets will only be used for the secondary objective #2.

19.2.3. Secondary Objective # 3

Objective – Electrical measurements (PCT and Impedance) at follow-ups

Pacing Capture Threshold (PCT) and impedance data will be collected using VectorExpress™. Pacing vector changes will be monitored for all implanted patients at follow-up visits.

Summary statistics for PCT and impedance at each time point (i.e. Implant, 6 months, etc.). The distribution of the electrical measurements at the final programmed pacing vector will be presented as n, mean, standard deviation, minimum, median and maximum. In the event of a replacement of a Medtronic Quad CRT-P or CRT-D device and/or the implanted LV lead, only measurements from the

Attain Stability Quad MRI SureScan LV Lead (Model 4798) implanted at the initial implant procedure will be included in the analysis cohort for this objective.

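### For the 37-patient fixation prior, the weight formula in Section 19.2.2 does not deliver the near-zero borrowing that the text promises when the new lead's observed rate is worse

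*Protocol*

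**What the plan says.** Secondary Objective #2 (Protocol, Section 19.2.2) estimates 6-month lead failure modes and borrows historical data through a power prior. There are two historical sets, each with its own weight. For fixation (helix) complications the set is "Data from the 37 patients who completed 6-month follow up with a successfully implanted 20066 lead". For all other lead complications it is "Data from the 401 patients who completed 6-month follow up in the Attain Performa 4298 study", scaled down to at most 37 effective patients.

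The Statistical Analysis Methods text describes the safeguard without qualification and just before noting that there are two weights, so it covers both groups: if the new lead "performs worse than historical data, the historical data will receive very little or zero weight".

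The formula follows. Each rate gets a Beta posterior from a uniform prior, p is the posterior probability that the current rate does not exceed the historical one, and the weight is a0 = 1 - exp(-(5p)^2). The text says that discounting begins below p of about 0.5 and is complete only as p goes to zero. Table 17 tabulates a0 at five values of p. The design intent is stated as "it penalizes an optimistic prior while not penalizing a pessimistic prior". Figure 8, the only illustration of a prior losing almost all its weight, uses the 401-patient set.

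**The concern.** The sentence promises an outcome (worse performance, so almost no borrowing), while the formula responds to p. The two coincide only when the data can show that performance is worse. With 37 historical patients the historical posterior is wide, so p stays well above zero when the observed current rate is about double the historical one, or is 3% against no historical events. The weight then stays high. In effect the rule treats a lack of evidence of disagreement as agreement.

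The helix is the active-fixation feature that separates this lead from the Attain Performa design. A reader of Section 19.2.2 would expect the fixation estimates to be essentially unborrowed if the new lead's observed rate were above history. They would instead be pulled towards a more favourable prior, which is what the safeguard is said to prevent.

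**Working it through.** **Inputs.** From Section 19.2.2: historical fixation sample 37; comparison sample 401; current sample 363 to 400; the two Beta posteriors, p and a0. *Assumption:* the historical number of fixation complications, y_h, is not in the protocol, so 0 to 3 of 37 are tried.

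**Step 1: reproduce Table 17.** a0 = 1 - exp(-(5p)^2) gives 0.002, 0.061, 0.221, 0.632 and 0.998 at p = 0.01, 0.05, 0.1, 0.2 and 0.5. Multiplying by 37/401 gives 0.000, 0.006, 0.020, 0.058 and 0.092. All ten entries match. At p = 0.2 the probability that the new lead is worse is 1 - 0.2 = 80%, yet 63% of the weight remains. This step needs no assumption about y_h. No scaling applies to the fixation set, because its actual and maximum effective sizes are both 37.

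**Step 2: find p for the 37-patient prior.** p = P(theta_c <= theta_h) is obtained by numerical integration, with theta_c ~ Beta(y_c + 1, n_c - y_c + 1) and theta_h ~ Beta(y_h + 1, 37 - y_h + 1). With 363 current patients:

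| Historical | Current | p | a0 | Patients borrowed (37 x a0) |
|---|---|---|---|---|
| 0/37 | 11/363 (3.0%) | 0.298 | 0.892 | 33 |
| 0/37 | 15/363 (4.1%) | 0.198 | 0.624 | 23 |
| 0/37 | 29/363 (8.0%) | 0.045 | 0.050 | 2 |
| 1/37 (2.7%) | 22/363 (6.1%) | 0.315 | 0.916 | 34 |

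**Step 3: locate the change of regime, with 400 current patients.**

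| Historical events of 37 | a0 at least 0.9 up to | a0 at least 0.5 up to | a0 at most 0.05 from |
|---|---|---|---|
| 0 (0%) | 2.75% | 4.5% | 8.0% |
| 1 (2.7%) | 6.0% | 8.25% | 12.5% |
| 2 (5.4%) | 9.0% | 11.5% | 16.5% |
| 3 (8.1%) | 12.0% | 14.75% | 20.0% |

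At 2/37 a full doubling (44/400, 11%) gives 0.63, so near-full borrowing at double the rate is not universal across the assumed counts.

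**Step 4: compare with a large prior.** For 11/401 against 24/400, p = 0.012 and the unscaled weight is 0.004. For 1/37 against 24/400, nearly the same pair of rates, p = 0.320 and the weight is 0.92. The promise holds in the setting that Figure 8 shows and fails in the one it does not.

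**Step 5: effect on the estimate.** Take 11/363 against 0/37, all fixation complications pooled, with a uniform starting prior.
- Current data only: Beta(12, 353), mean 12/365 = 3.29%, 95% interval 1.71-5.34%.
- With borrowing: 37 x 0.892 = 33.0 event-free patients are added, giving Beta(12, 386), mean 12/398 = 3.02%, 95% interval 1.57-4.90%.
- Width without borrowing relative to width with it: (5.34 - 1.71)/(4.90 - 1.57) = 3.63/3.33 = 1.09.

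**The case against.** The strongest reply is that the weighting behaves sensibly. If the true rate were 11/363, the chance of seeing 0/37 is (1 - 11/363)^37 = 32%. If it were 22/363, the chance of at most 1/37 is about 33%. A p near 0.3 reports correctly that 37 patients cannot separate these rates, and where evidence exists the penalty works (0.061 at p = 0.05, 0.002 at p = 0.01). The gradual decline is also disclosed in the listed characteristics of the loss function and in Table 17, which has its own column for the 37-patient set.

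This stands in part. It rules out a stronger reading that a reader might infer, that the rule borrows almost fully when the new lead is *clearly* worse. The excess is in observed rates only. It does not rescue the sentence, which is conditioned on performance and not on strength of evidence, and which the formula beneath it contradicts.

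Three other inferences are tempting but not supported:
- **That enrolment would shrink by a definite number** (33/0.85 = about 39). Section 19.2.2 has two weights and does not say which one enters the effective sample size of 400, or how they combine.
- **That restricting the historical set to implanted 6-month completers makes the prior optimistic.** This is conjecture about data not shown. The objective concerns post-implant failure modes, and Section 15.8.2.2 does not count an unsuccessful implant in itself as an adverse event.
- **That fixation borrowing should be removed from the effective sample size, or the historical set rebuilt.** The first is a design trade-off that would undercut the adaptive look, and the second needs data the protocol does not present.

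The planned intervals are also per failure mode, so the pooled interval in the working is an illustration and not the planned output.

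**Conclusion.** The point holds as a contradiction between a stated property and the formula meant to provide it, confined to the fixation group. Table 17 alone shows it, without any assumption. Its size depends on the unstated historical count: with 0 or 1 events of 37, observed rates of 3.0% or 6.1% keep about 89% or 92% of the weight, and weights of about 5% need observed rates near 8% or 12.5%. The pattern persists for 2 or 3 events, less sharply relative to the historical rate.

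The practical effect is modest. In the illustrated case the upper limit moves by 0.44 percentage points (5.34 - 4.90). Borrowing is capped at 37 patients, the objective has no performance requirement, and none of the primary objectives borrows. This is a statement worth correcting and a display worth adding. It does not threaten the trial's main conclusions.

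**What to change.** 1. Replace the sentence in Section 19.2.2. Say that the weight falls gradually with p, and that for the 37-patient fixation prior it stays high unless the observed current rate is several times the historical one.
2. Add a table of actual weights for the fixation prior at 0 to 3 historical events over a range of current rates, so that the 37-patient case is shown as well as the 401-patient case in Figure 8.
3. For each fixation-related failure mode, report the current-data-only credible interval beside the borrowed one.

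The cost is some rewording, one small table and one extra results column. The current-data-only intervals will be up to about 9% wider than the borrowed ones. The borrowing rule, the interim look and the planned enrolment are unchanged.

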19.3. Additional Analysis

19.3.1. Poolability Analysis

Additional analysis will be conducted to summarize study primary objectives by patient characteristics, such as gender, age group, race and study site geography. The purpose of the poolability analysis is to identify if there is any clinical meaningful difference in a subgroup of patients. These analyses will not be statistically powered, and there is no pre-specified statistical significance level for these analyses.

19.3.2. Sensitivity Analysis

All subjects enrolled into this study and successfully implanted with a Medtronic Quad CRT-P or CRT-D device and Attain Stability Quad MRI SureScan LV Lead (Model 4798) will be included in the primary efficacy analysis datasets (efficacy objectives #1 and #2). Sensitivity analysis such as the Tipping Point method or similar will be conducted to investigate the influence of subjects who were successfully implanted with the required system however missed a 6 month post implant follow-up test(s) (due to reasons such as missing in-office visit, subject exit, death and/or the initial implanted lead was deactivated). For this purpose, all subjects with successful implant who do not meet analysis cohort requirements, will be considered as the worst case scenario (i.e. failure to meet the efficacy endpoints). The results will be submitted as part of the clinical reports.

19.3.3. Additional Data Collection

Heart failure clinical outcomes will be assessed. The measurements, including NYHA classification, death, heart failure related hospitalization, heart failure related study exits and subject self-reported global assessment for each subject will be obtained at 6 months post-implant. Summary statistics will be provided.

19.3.3. Overall Study Sample Size Requirements

The sample size requirement at 6-months for each of the study objectives is displayed in Table 18. The first row does not account for attrition, while the second row is inflated by 15% attrition. The sample size for Secondary Objective #2 assumes the conservative case that the interim look results in, no borrowing of historical data. Therefore, the overall sample size for the study is 471.

Table 18: Required Sample Size by Study Objective

	Primary Safety Objective	Primary Efficacy Objective #1	Primary Efficacy Objective #2	Secondary Objective #1	Secondary Objective #2 (post-implant failure modes)	Secondary Objective #3	Overall
Number needed at 6-months	170	145	50	NA	400	NA	400
Number of enrollments	200	171	59	NA	471	NA	471

20. Ethics

20.1. Statement(s) of Compliance

This study will be conducted in compliance with international ethical and scientific quality standards, known as good clinical practice (GCP). Good Clinical Practice includes review and approval by an independent IRB/EC before initiating a study, continuing review of an ongoing study by an IRB/EC, and obtaining and documenting the freely given IC of a subject before initiating the study.

The clinical investigation shall not begin until all required approvals and documents from the IRB/EC and a regulatory authority, if needed, have been received. Any additional requirements imposed by the IRB/EC or regulatory authority shall be followed, if appropriate.

The Attain Stability Quad Clinical Study was designed to reflect the GCP principles outlined in ISO 14155:2011 and other international clinical requirements outlined below. These include the protection of the rights, safety and well-being of human subjects, controls to ensure the scientific conduct and credibility of the clinical investigation and the definition of responsibilities of the sponsor and investigators. In accordance with ISO 14155:2011, the sponsor shall avoid improper influence on, or inducement of, the subject, monitor, any investigator(s) or other parties participating in, or contributing to, the clinical investigation. All investigators shall avoid improper influence on or inducement of the subject, sponsor, monitor, other investigator(s) or other parties participating in or contributing to the clinical investigation. Adverse Event and Device Deficiency handling in the Attain Stability Quad Clinical Study is ISO 14155:2011 compliant for all participating geographies with the exception that only those AEs which are related to the subject's system, procedure, accessory, or are cardiovascular-related, and all Serious AEs, will be collected. This ensures any AEs which could potentially be relevant will be collected. The scope and duration of the Attain Stability Quad Clinical Study would make collection of all AEs to be a significant burden for investigators and investigative sites. Therefore, only a subset of AEs will be collected in this study, including any that could be potentially relevant.

The principles of the Declaration of Helsinki have been implemented through the IC process, IRB/EC approval, study training, clinical trial registration, pre-clinical testing, risk-benefit assessment and publication policy.

Ultimately, all sites in all geographies will follow and comply with:

- Principles of Declaration of Helsinki
- 21 CFR Part 11 (Electronic Records, Electronic Signatures) (per local law)
- 21 CFR Part 54 (Financial Disclosure by Clinical Investigators)
- The Clinical Trial Agreement
- The procedures described within this CIP
- Local Ethics Board Requirements

In addition to the regulatory requirements outlined above, the study will be conducted according to federal, national and local laws, regulations, standards, and requirements of the countries/geographies where the study is being conducted. These include but are not limited to:

- In the United States, the study will be conducted under an FDA IDE in compliance with 21 CFR Parts:
 - 50: Protection of Human Subjects
 - 56: Institutional Review Boards
 - 812: Investigational Device Exemptions
- In Canada, SOR/98-282, Section 59-88 will be followed and Mandatory Problem Reporting 59(1), 59(2), 60 (1)).
- In EMEA the study will be conducted in compliance with the Active Implantable Medical Device Directive (AIMDD), Declaration of Helsinki version 2013, and full compliance with ISO 14155.
- In Hong Kong and Malaysia, the study will be conducted in compliance with the Declaration of Helsinki version 2013.
- In EMEA, an IB is not required for this study as it is a post market study

The study will be publicly registered prior to first enrollment in accordance with the 2007 Food and Drug Administration Amendments Act FDAAA and Declaration of Helsinki on <http://clinicaltrials.gov> (PL 110-85, section 810(a)). In addition, the study may be registered in local regulatory databases where required by local law.

Approval of the CIP and CIP amendments is required from the following groups prior to any study procedures at a study site:

- Medtronic
- Principal Investigators (where required by local law/regulations)
- Geography-specific regulatory authorities (if regulatory approval is required)
- An independent medical ethics committee or institutional review board.

Similarly, approval of subsequent revisions to the CIP is required at each study site from the above mentioned groups prior to implementation of the revised CIP at the site.

21. Study Administration

